9.3.3.2 Secondary endpoints

PGIC at Week 48

PGIC is a single-item rating scale. Patients will be asked to rate their overall status relative to baseline: 1 = Very much improved, 2 = Much improved, 3 = Minimally improved, 4 = No change, 5 = Minimally worse, 6 = Much worse, 7 = Very much worse. The PGIC is measured at weeks 4, 12, 24, 36 and 48. Missing values are treated as missing.

Change from baseline in whole-body (WB) longitudinal composite muscle fat infiltration (MFI) (B muscles) at Week 48

This endpoint is derived for B-muscles as described in 9.3.1.3, where Y=MFI.

Relative change from baseline in average shoulder abductor strength by hand-held quantitative dynamometry at Week 48

Shoulder abductor strength is measured three times on each arm at baseline, weeks 4, 12, 24, 36, and 48, and a mean value is recorded in the EDC. At each timepoint, the average mean for the two arms will be derived, and a relative change of this average from baseline will be derived as specified in 9.2. above.

Missing values will be treated as missing.

[figure not shown]
Change from baseline in Neuro-QoL-UE Function at Week 48

[figure not shown]
The Neuro-QoL-UE is a 20-item questionnaire, from which a single scale is derived. It is measured at baseline and at weeks 4, 12, 24, 36 and 48. The Neuro-QoL-UE measures ability across fine motor and activities of daily living involving digital, manual, and reach-related function and self-care. Responses are divided into 5 ordinal levels (1 = unable to do, 2 = with much difficulty, 3 = with some difficulty, 4 = with a little difficulty, 5 = without any difficulty). The endpoint is derived as:

[figure not shown]
$$20 \times (\text{Sum scores from all items answered}) / (\text{Number of items answered})$$

[figure not shown]
The Neuro-QoL-UE will be recorded as missing if fewer than 10 items are answered. The score ranges from 20-100, with higher scores reflecting better upper extremity fine motor function.

Change from baseline is derived as specified in 9.2. above.

[figure not shown]
Change and relative change from baseline in muscle strength by hand-held quantitative dynamometry

There are eight dynamometry outcomes measured at baseline and at weeks 4, 12, 24, 36 and 48. They relate to 4 assessment areas:

- [1] Average dominant shoulder abductor strength (kg)
- [2] Average non-dominant shoulder abductor strength (kg)
- [3] Average dominant hand grip strength (kg)
- [4] Average non-dominant hand grip strength (kg)
- [5] Maximum dominant shoulder abductor strength (kg)
- [6] Maximum non-dominant shoulder abductor strength (kg)
- [7] Maximum dominant hand grip strength (kg)
- [8] Maximum non-dominant hand grip strength (kg)
- [9] Average shoulder abductor strength (kg)
- [10] Average hand grip strength (kg)
- [11] Total average muscle strength (kg)

[1] to [8] are variables in the dataset which need to be mapped from left and right to dominant/non-dominant for each patient. [9] and [10] are the means of [1]-[2] and [3]-[4] respectively. [11] is the mean of [9]-[10]. If either [9] or [10] is missing, [11] becomes missing. Change from baseline and relative change from baseline will be derived for all 11 measures (as specified in 9.2. above).

Missing values will be treated as missing.

Sub-Neuro-QoL

A sub-scale called Sub-Neuro-QoL will be derived for the purpose of exploratory analysis, using the following five items from the Neuro-QoL-UE: NQUEX03 (using a spoon); PAF9 (picking up clothes); PFA47 (pulling up trousers); NQUEX04 (putting on a shirt); and NQUEX05 (taking off a shirt). This is derived as:

$$5 \times (\text{Sum scores from all items answered}) / (\text{Number of items answered})$$

The Sub-Neuro-QoL will be recorded as missing if fewer than 3 items are answered. The score ranges from 5-25, with higher scores reflecting higher independence in performing tasks.

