2.4.2 Multiple testing strategy

To control the overall type I error rate, the primary endpoint and secondary efficacy endpoints will be tested in sequence as follows:

1. The primary endpoint will be tested at 2-sided significance level $\alpha=0.05$.
2. If a statistically significant result is obtained for the primary endpoint (test 1), change from baseline in WB longitudinal composite MFI in B muscles at Week 48 and relative change from baseline in average shoulder abductor strength by hand-held quantitative dynamometry at Week 48 will be tested using the Bonferroni procedure, i.e., each will be tested at 2-sided $\alpha = 0.025$ (test 2).
 - If both tests are significant, a statistically significant result is obtained from test 2. The remaining significance level from test 2 = 0.05.
 - If only one of the 2 tests is significant, a statistically significant result is obtained from test 2. The remaining significance level from test 2 = 0.025.
 - If neither test is significant, a statistically significant result is not obtained from test 2.
3. If a statistically significant result is obtained from test 2, PGIC at Week 48 will be tested at the remaining significance level from test 2 (test 3).
4. If a statistically significant result is obtained from test 3, change from baseline in Neuro-QoL-UE at Week 48 will be tested at the remaining significance level from test 3, which is equal to the remaining significance level from test 2.

In recognition of the complexities of this rare disease and the novelty of this research field, in case the result of the primary analysis (MMRM) of the primary endpoint is on the boundary of statistical significance, but at least one of the following is true:

- results from most sensitivity analyses are nominally significant,
- result of PGIC at Week 48 is nominally significant,
- result of Change from baseline in WB longitudinal composite MFI in B muscles at Week 48 is nominally significant,

AND

- results from most of the remaining secondary and exploratory efficacy endpoints are directionally favorable to losmapimod,

the totality of evidence will be utilized to support the decision making.

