9.2 BASELINE AND CHANGE FROM BASELINE

For all endpoints, the baseline value is defined as the last non-missing value obtained prior to the first dose of study treatment.

For continuous laboratory variables, electrocardiogram (ECG) data and vital signs, if two visits are equally eligible to assess patient status at baseline (e.g., screening and baseline assessments both on the same date prior to first dose with no washout or other intervention in the screening period), the average will be used as the baseline value. In the scenario where there are two assessments on day 1, one with time recorded and the other without time recorded, the one with time recorded will be selected as baseline. Where safety data will be summarized over time, time on study will be calculated in relation to date of first study treatment.

In all summaries, change from baseline variables will be calculated as the post-treatment value minus the value at baseline. The percentage change (relative change) from baseline will be calculated as:

$$100 \times (\text{Post-baseline value} - \text{Baseline value}) / (\text{Baseline value})$$

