9.3 DERIVED AND TRANSFORMED DATA

9.3.1 General derivations

9.3.1.1 Average

Where an average is required, but some data are missing, the average is the mathematical mean of the non-missing value(s).

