9.3.3 Efficacy derivations

9.3.3.1 Primary endpoint

Change from baseline in average total RSA Q1-Q5 with 500 g wrist weight at Week 48, where the average is applied over both arms.

The RWS (total RSA Q1-Q5) measurements required for the analysis of the primary endpoint are those assessed at baseline and at weeks 4, 12, 24, 36 and 48, on both the dominant and non-dominant arms. At each visit the RWS for each arm (Left and Right) is the sum of the 5 RSA measurements: Q1+Q2+Q3+Q4+Q5, where the weight used is 500g. The average total RSA is the average of the two totals:

Average = Mean of (Total for Left Arm with 500g weight, Total for Right Arm with 500g weight)

Change from baseline is derived as specified in 9.2. above.

Note: the average over both arms per visit needs to be calculated before computing changes from baseline.

If an arm is not tested for RWS, and the reason code is W='Weakness related', then the RWS for that arm should be imputed as 0.

Because the RWS data are used in the primary endpoint analysis for this study, Fulcrum or its designated vendor will perform additional cleaning of these data. Fulcrum or its designated vendor will use the following criterion to identify potentially invalid data points: post-baseline data points that show a change (increase or decrease) >50% from the previous result on total RSA Q1-Q5. Records meeting this criterion will be sent to the RWS vendor for further investigation. After blind review, the RWS vendor will communicate to Fulcrum or its designated vendor any records that are deemed invalid because of problems with the software and should therefore not be included in the analysis. These rare sessions, if any, will be flagged by the RWS vendor, and their associated results, including total RSA Q1-Q5, total RSA Q1-Q4, sum of Q1 and Q3, and all 5 individual quadrants, will be removed from the RWS analysis (also see 9.3.3.3).

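### When one arm is missing, the shoulder strength endpoint compares a one-arm value with a two-arm baseline, which falsely raises the change if the weaker arm is the missing one

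*SAP*

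**What the plan says.** - **Endpoint.** SAP 9.3.3.2, shoulder abductor strength: "At each timepoint, the average mean for the two arms will be derived". The relative change is then taken on that average by the formula in SAP 9.2, which is 100 x (post-baseline - baseline) / baseline.
- **Missing values, this endpoint.** SAP 9.3.3.2: "Missing values will be treated as missing". Nothing is said about one arm being present and the other absent.
- **Missing values, any average.** SAP 9.3.1.1, a general derivation: "Where an average is required, but some data are missing, the average is the mathematical mean of the non-missing value(s").
- **The one override.** In the list of dynamometry measures later in SAP 9.3.3, total strength [11] has its own rule: "If either [9] or [10] is missing, [11] becomes missing". Average shoulder abductor strength [9] has none.
- **The RWS rule.** SAP 9.3.3.1, for an arm not tested with the weakness reason code: "then the RWS for that arm should be imputed as 0". There is no counterpart for dynamometry.
- **Role of the endpoint.** SAP 2.4.2 puts it in test 2 with whole-body MFI: the pair "will be tested using the Bonferroni procedure", each at 2-sided 0.025. A significant result on either allows PGIC to be tested, and then Neuro-QoL-UE.
- **Conduct of the test.** Protocol 6.1.3 describes isometric dynamometry and leaves further detail to a study reference manual.

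**The concern.** The general averaging rule is harmless when the parts of an average are interchangeable. The two shoulders need not be: the protocol background says asymmetric muscle involvement is common in FSHD. Eligibility restricts reachable workspace in the dominant arm only, so the other arm may be much weaker or stronger.

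If one arm drops out of the Week 48 average but is in the baseline average, the relative change mixes true change with the baseline difference between arms. When the weaker arm is the missing one, the mixture is upward, and a patient who lost strength can be ranked among those who gained it.

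The endpoint is alpha-protected, has the lowest stated power in SAP section 5, and can open the way to two patient-reported endpoints. Its sensitivity analyses in SAP 10.2.2.3 (on-treatment data; correct repeat category) do not examine a missing arm. The multiple imputation in SAP 10.2.1.2 is for the primary endpoint.

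**Working it through.** **1. The plan's own figure.** Inputs from SAP section 5: 105 FSHD1 patients per group, 10% missing at Week 48, difference 20.2, SD 46, 2-sided Wilcoxon at 0.025, power at least 75%.

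- Patients with data: 105 x 0.9 = 94.5 per group. With Wilcoxon efficiency 3/pi: 94.5 x 0.955 = 90.2.
- Standard error: 46 x sqrt(2/90.2) = 6.85. 20.2/6.85 = 2.95. 2.95 - 2.24 = 0.71, so power is 0.76.
- Simulated Wilcoxon power is 0.749 with 94 per group and 0.761 with 95. The stated 75% reproduces.

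**2. Scores for a patient with one arm missing.** Let a be the stronger arm at baseline, b the weaker, and d the proportional loss in the stronger arm. The weaker arm is missing at Week 48.

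- SAP rule: 100 x [a(1-d) / ((a+b)/2) - 1]
- Same arm at both times: -100d
- Lost arm scored 0 kg: 100 x [a(1-d) / (a+b) - 1]

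**3. Illustration (assumed values).** a = 6 kg, b = 2 kg, d = 0.10. The baseline average is 4 and the remaining arm is 5.4.

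- SAP rule: 5.4/4 - 1 = +35%
- Same arm: 5.4/6 - 1 = -10%
- Lost arm 0 kg: 2.7/4 - 1 = -32.5%

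**4. Range, remaining arm unchanged (arm values assumed).** The same-arm rule gives 0% in every row.

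| Baseline (kg) | SAP rule, weaker arm missing | Weaker arm scored 0 | SAP rule, stronger arm missing |
|---|---|---|---|
| 6 and 6 | 0.0% | -50.0% | 0.0% |
| 6 and 4 | +20.0% | -40.0% | -20.0% |
| 6 and 3 | +33.3% | -33.3% | -33.3% |
| 6 and 2 | +50.0% | -25.0% | -50.0% |
| 6 and 1 | +71.4% | -14.3% | -71.4% |

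With d = 0 the SAP score is 100(a-b)/(a+b). It passes 20.2 when a/b exceeds 1.202/0.798 = 1.51. An arm missing at baseline and present later gives the mirror-image error.

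**5. Effect on the test (illustrative).** Assumptions: 94 per group; patients with both arms follow the SAP's difference and SD; in the rest, the weaker arm is missing and the stronger unchanged. The arm-loss rates and arm ratios are not in the documents.

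| Arm loss, losmapimod / placebo | Arm ratio | Power, SAP rule | Average set to missing | Lost arm 0 |
|---|---|---|---|---|
| 2% / 5% | 2:1 | 68% | 74% | 79% |
| 2% / 5% | 3:1 | 64% | 73% | 78% |
| 5% / 10% | 2:1 | 61% | 71% | 80% |
| 5% / 10% | 3:1 | 53% | 71% | 79% |

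At 1% / 2% the SAP rule gives about 72 to 73%, against about 75% with no arm loss. The last column can exceed 75% because the assumed difference in arm loss then counts as treatment effect.

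With no treatment effect and equal arm loss of 2%, 5% or 10% (ratio 3:1), the SAP rule rejects in 2.7%, 2.6% and 2.2% of trials, against 2.5% nominal.

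**The case against.** **A reader might infer that the plan scores progression to an untestable arm as improvement.** The documents do not go that far. Neither says that an arm too weak to test is entered as missing. Isometric dynamometry involves no movement, so a near-zero force can itself be a reading, whereas the primary RWS test needs the arm to move with a 500 g weight. The lack of a zero rule may reflect that difference, and the manual may require 0 kg. If it does, the weakness case does not arise. The mismatch remains for an arm missing for any other reason.

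**A reader might also infer a false-positive risk in favour of losmapimod.** That is not supported either. If the drug slows progression, placebo patients lose more arms and collect more false gains, so the error costs power. With equal arm loss and no effect, rejection stays near nominal. It rises to 3.3% (ratio 2:1) or 4.1% (3:1) if losmapimod patients lose arms at 10% against 5% with no effect in the others, but that is not the null of an inert drug.

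**The text may mean something else.** The endpoint's missing-value sentence could be read as making the whole average missing. The explicit override for [11] points the other way: it would be needless if averages already became missing. On that reading, patients who lost an arm to weakness would leave the analysis at that visit, which is informative missingness.

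**The example is severe.** The protocol background gives strength loss of about 1% to 4% a year. The arm weights are chosen, one patient's score is not comparable with a group difference of 20.2, and the test uses ranks. All of this stands. It limits the likely size but does not remove the mismatch.

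**Conclusion.** The concern holds as a fault in a stated rule. SAP 9.3.1.1 and 9.3.3.2 together compare one arm with a two-arm baseline, and no override or listed sensitivity analysis deals with it.

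The error is upward when the weaker of two unequal arms is missing, nil when the arms are equal, and downward when the stronger arm is missing. In the assumed 6 and 2 kg case the score is +35%, against -10% on a like-for-like basis.

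The effect on the trial cannot be stated from the documents, because they give neither the rate of arm loss nor the degree of asymmetry. Under the assumptions shown, power falls from about 75% to between 72-73% and 53%. The likely harm, if losmapimod works, is a missed result on this endpoint.

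**What to change.** In SAP 9.3.3.2, override 9.3.1.1 for average shoulder abductor strength:

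1. When one arm is missing at baseline or at a visit, compute both the baseline and the visit value from the same arm(s).
2. Where the data record that an arm was not tested because of weakness, score it 0 kg, as 9.3.3.1 does for RWS.
3. State how the dynamometry manual has an arm too weak to test recorded: as missing or as 0 kg.

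The cost is a few sentences before unblinding. The first rule uses data already collected and needs no reason code, but it ignores what happened to the lost arm. The second keeps that information but depends on a reason being recorded, which the documents do not show for dynamometry.

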9.3.4 Safety derivations

9.3.4.1 Adverse events

Adverse events (AEs) and serious adverse events (SAEs) will be collected from the time of signature of the informed consent form (ICF), until after either the 7-Day follow-up period is completed or up to 30 days after the patient has stopped study treatment, whichever is later.

All AEs and SAEs are recorded in the Adverse Event Form.

A treatment-emergent AE (TEAE) is defined as an AE that meets any of the following conditions:

- begins on or after the first dose of study drug and on or before the stop of study drug + 35 days
- begins before the first dose of study drug and worsens on or after the first dose of study drug and on or before the stop of study drug + 35 days
- is completely missing an onset date and end date
- is completely missing an onset date and the end date is on or after the first dose of study drug and on or before the stop of study drug + 35 days.

REACH TRIAL

Stop of study drug is recorded in the End of Treatment form as the Date of Last Dose.

Missing start and stop dates for TEAEs will be handled as follows:

- ??-MMM-YYYY: If the AE month and year are different from the month and year of the first dose of study drug, assume 01-MMM-YYYY. If the month and year are the same as the first dose of study drug month and year and the AE end date (after any imputation) is on or after the first dose of study drug, then assume the date of the first dose of study drug. If the AE month and year are the same as the first dose of study drug month and year and the AE end date (after any imputation) is prior to the first dose of study drug, then assume the end date for the onset date.
- DD-???-YYYY/??-??-YYYY: If the AE year is different from the year of first dose of study drug, assume DD-JAN-YYYY/01-JAN-YYYY of the collected year. If the AE year is the same as the first dose of study drug year (and in the case of AEs that are non ongoing the AE end date (after any imputation)) is on or after the first dose of study drug, then assume the date of the first dose of study drug. If the year is the same as the first dose of study drug and the AE end date (after any imputation) is prior to the first dose of study drug, then assume the end date for the onset date.

Missing end dates:

- ??-MMM-YYYY: Assume the last day of the month
- DD-???-YYYY: Assume DD-DEC-YYYY
- ??-???-YYYY: Assume 31-DEC-YYYY.

If the imputed end date is greater than either the study cutoff date or date of death, then assume the minimum of study cutoff date and date of death.

The following classifications are contained within the eCRF and do not require derivation:

- MedDRA version 24.1 or higher coding of System Order Class (SOC) and Preferred Term (PT)
- Common Terminology Criteria for Adverse Event (CTCAE) grade version 5.0
- Classification of AEs as SAEs
- SAE criteria
- Relationship of AEs
- AE of special interest (AESI)
- Outcome
- Action taken

An AE is deemed related to study drug if it is classified as Possibly, Probably or Definitely related. AEs that have missing relatedness (after data querying) will be assumed to be related to study treatment.

Severity of AE is derived from CTCAE coding. Codes 1 and 2 represent Mild and Moderate severity, respectively, and codes 3-5 represent Severe severity. Where CTCAE code is missing, severity will be categorized as Missing.

AESI are defined as potential drug-induced liver injuries. These will be derived from laboratory liver tests where:

- (1) A patient has ($ALT \geq 3^*ULN$) and ($Total\ bilirubin \geq 2^*ULN$) and ($ALP < 2^*ULN$) or;
- (2) A patient has ($AST \geq 3^*ULN$) and ($Total\ bilirubin \geq 2^*ULN$) and ($ALP < 2^*ULN$)

where ALT = alanine aminotransferase; ALP = alkaline phosphatase; ULN = upper limit of normal; and AST = aspartate aminotransferase.

These should also be recorded in the EDC as AEs, but this source will not be used to identify AESIs.

